### 6.2.1.1. CMI analysis

The analysis will be performed on each group separately, pooled placebo group and pooled RSV group. All the CMI analysis will be performed for each peptide pool (F, N, M2-1) separately and taking all the peptide pool together for subjects who has data available for the three peptide pools.

With respect to secondary objectives, the following parameters will be summarized by group using descriptive statistics (N, geometric mean [GM], minimum [min], 1st quartile [Q1], median, third quartile [Q3], maximum [max]), at each timepoint during which blood samples are collected for CMI in investigational sites with a laboratory in proximity capable to perform WBS necessary for the CMI assay:

- Frequency of CD4+ T-cells expressing at least two markers among CD40L, IL-2, TNF- $\alpha$ , and IFN- $\gamma$  upon stimulation with F, N and M2-1.
- Box plot with individual data for CD4+ T-cells expressing at least two markers among CD40L, IL-2, TNF- $\alpha$ , and IFN- $\gamma$  upon stimulation with F, N and M2-1 and combined peptide pool will be presented.

With respect to tertiary objectives, the cellular immune response will be further characterized using descriptive analysis of the frequency of CD8+ T-cells and CD4+ T-helper cell profile (Th1, Th2, Th17) expressing at least one or any combination of marker(s) among CD40L, 41BB, IL-2, TNF- $\alpha$ , IFN- $\gamma$ , IL-13, and IL-17.

The following parameters will be summarized by group using description statistics (N, GM, min, Q1, median, Q3, max), at each timepoint during which blood samples are collected for CMI:

- Frequency of CD4+ and CD8+ T-cells expressing at least one or any combination of immune marker(s) among CD40L, 41BB, IL-2, TNF- $\alpha$ , IFN- $\gamma$ , IL-13 and IL-17 upon stimulation with F, N and M2-1 peptide pools.
- Tabular presentation of T-helper cell 'Th1' profile - Frequency of CD4+ T-cells expressing at least IFN- $\gamma$  but no IL-13 upon stimulation with F, N and M2-1 peptide pools.
- Tabular presentation of T-helper cell 'Th2' profile: Frequency of CD4+ T-cells expressing at least IL-13 but no IFN- $\gamma$  upon stimulation with F, N and M2-1 peptide pools.
- Tabular presentation of T-helper cell 'Th17' profile - Frequency of CD4+ T-cell expressing atleast IL17 upon stimulation with F, N and M2-1 peptide pools.
- Calculation of 'Th2/Th1 ratio' = Frequency of Th2 T-cells / frequency of Th1 T-cells.
- Separate box plot with individual data for CD4+ and CD8+ T-cells expressing at least one marker among CD40L, 41BB, IL-2, TNF- $\alpha$ , IFN- $\gamma$ , IL-13 and IL-17 upon stimulation with F, N and M2-1 and combined peptide pools will be presented.

- Separate box plot with individual data for CD4+ T-cells expressing at least IFN- $\gamma$  but no IL-13 (Th1 profile) upon stimulation with F, N and M2-1 and combined peptide pools will be presented.
- Separate box plot with individual data for CD4+ T-cells expressing at least IL-13 but no IFN- $\gamma$  (Th2 profile) upon stimulation with F, N and M2-1 and combined peptide pools will be presented.
- Separate box plot with individual data for CD4+ T-cells expressing at least IL17(Th17 profile) upon stimulation with F, N and M2-1 and combined peptide pools will be presented.

The need to generate co-expression profile graph for any combination for CD4+ and CD8+ will be evaluated after looking at the descriptive tables.

#### **6.2.1.2. Humoral immune response**

For each group, at each timepoint that blood samples are collected for humoral immune response against the investigational RSV vaccine (neutralizing antibody titers against RSV-A, RSV F antibody concentrations, and palivizumab-competing antibody concentrations):

- GMTs/GMCs will be tabulated with 95% CI and represented graphically.
- Percentage of subjects above the seropositivity threshold will be tabulated with exact 95% CI.
- Antibody titers/concentrations will be displayed using reverse cumulative curves.
- The distributions of neutralizing antibody titers/concentrations will be tabulated (< 128, 128-256, > 256-512, > 512-1024, > 1024-2048, > 2048-4096, > 4096)
- Percentage of responders in terms of RSV-A neutralizing antibody titers will be tabulated with exact 95% CI.
- Individual post-vaccination versus pre-vaccination results will be plotted using scatter plots. Results of the Placebo groups will be used as a reference.
- Geometric mean of ratios of antibody titers/concentrations at each post-vaccination timepoint over pre-vaccination will be tabulated with 95% CI.
- Distribution of the fold increase of the neutralizing antibody titers will be tabulated by pre-vaccination titer category (percentage of subjects with a fold increase equal to or above 1, 2, 2.5, 3, 4, 6, 8, 10, 11 and 12 by pre-vaccination titre category: (< 128, 128-256, > 256-512, > 512-1024, > 1024-2048, > 2048-4096, > 4096, and by cumulative category: <128,  $\geq$ 128,  $\geq$ 256,  $\geq$ 512,  $\geq$ 1024,  $\geq$ 2048,  $\geq$ 4096.).
- The kinetics of individual antibody titer/antibody concentration results will be plotted as a function of time for subjects with results available at all timepoints.

If available, any further exploratory immunology results (including, but not limited to anti-vector immunity) will be reported by group and timepoint using descriptive summary statistics will be described separately in Additional analysis request (AAR).

### 6.3. Analysis of RSV incidence

The assessment of RSV analysis incidence and severity will be performed on the Exposed Set on RSV groups, placebo groups, pooled RSV and pooled Placebo groups separately for first RSV season (Day 1-366) and second RSV season (Days 367-731) and overall (Days 1-731).

The analysis will be performed according to all case definitions presented in [Table 5](#).

The proportion of subjects with at least one RSV infection and number of infections experienced by subjects meeting each of the case definition in [Table 5](#) (with 95 % CI) will be calculated by group.

The number of RSV infections within each group and the maximum disease severity of the event will be tabulated. The number of RSV infections within each group and frequency of hospitalization will be tabulated. The number of infections in each group and descriptive analysis of the viral load associated with the maximum disease severity of the event will be tabulated (mean, median, min, max). Descriptive analysis on maximum viral load per subject based on qRT-PCR confirmed RSV infection of maximum severity will be performed.

The viruses identified in the Respiratory Viral Panel will be tabulated to those events where RSV-RTI was identified to describe frequency of co-infections and responsible viruses. These tables will be repeated limited to RVP results of cases of confirmed LRTI and RSV-LRTI.

After looking at the frequency of coinfection of all confirmed LRTI and RSV-LRTI, if there will be more than 10% coinfections (RSV infection with identification of another viral pathogen on RVP), tables will be reproduced including those RSV episodes where co-infection was present and those where no other respiratory viral pathogen was identified. The descriptive analysis on viral load table will not be repeated on subject with at least one episode with maximum viral load.

Listing will be presented for all cases of RSV infection until Day 731 with the details of gender, age at episode, country, site, day of event (i.e days since first visit), classification according to maximum severity of episode as RSV RTI/RSV LRTI/ RSV severe LRTI and RSV very severe LRTI, RSV hospitalization 'Yes/No', SpO2 value, respiratory rate, result of RSV qRT-PCR and RVP result will be presented.

Listings will be generated at Day 731 for all hospitalized cases with gender, age at episode, classification according to maximum severity of episode as (RSV RTI/RSV LRTI/ RSV severe LRTI and RSV very severe LRTI), RVP result, total number of calendar days on which the child was hospitalized, days requiring monitoring/nursing observation, days requiring nasogastric or intravenous fluids, days requiring supplemental oxygen, days requiring respiratory support excluding mechanical ventilation, days requiring mechanical ventilation and days requiring pediatric intensive care unit management.

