9.2.1. Passive surveillance

All subjects' parent(s)/LAR(s) will be instructed to contact investigator/study staff in case of any new RTI symptoms (cough, runny nose or blocked nose) or in case of any new difficulty in breathing or wheezing. They will be also reminded to record the start date and the end date of RTI symptoms on the RTI episode card.

- **If there is** any new difficulty in breathing, wheezing or parental concern, the investigator/study staff will schedule an assessment visit as soon as possible (refer to Section 9.2.4), but no later than 24 hours after the phone contact to ensure prompt assessment of the need for medical care.
- **If there is no suspicion** of difficulty in breathing, nor wheezing, nor parental concern, but there are any new symptoms of an RTI (cough, runny nose or blocked nose), the investigator/study staff will schedule an assessment visit as soon as possible (refer to Section 9.2.4), but no later than 72 hours after the phone contact. Performing the visit as soon as possible is important to assess the need for medical care, to ensure that early symptoms are captured, and also to collect an optimal nasal swab for the detection of RSV.
- All passive surveillance contacts will be document in the eCRF.
- In the event that it is not possible to schedule an assessment visit, which may arise if the family have travelled, then the assessment visit page of the eCRF should be filled in as completely as possible using available medical records.

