11.10. Analysis of RTI and LRTI

The analysis will be performed on the TVC on two pooled groups (i.e. pooled RSV and pooled Placebo) separately for first and second RSV seasons and overall.

The proportion of subjects with at least one RSV-associated RTI (with 95 % CI) will be calculated. The same descriptive analysis will be performed for subjects with at least one RSV-associated LRTI and those with at least one RSV-associated severe LRTI.

As primary analysis, the assessment of RSV infection will be performed using the quantitative RT-PCR according to standardized case definitions (see [Table 4](#)) based on the available WHO case definitions.

Descriptive analyses (mean, median, min, max) of viral load assessed by the quantitative RT-PCR (RSV-A/B) of RSV-RTI, RSV-associated LRTI and severe LRTI cases will be tabulated. This analysis will also be done by study group.

The incidence rate of all-cause RTI (with 95% CI) will be calculated by group. The same descriptive analysis will be performed for all cause LRTI and all cause severe LRTI. These will also be presented for each viral etiology identified by multiplex PCR.

The incidence rate of asymptomatic RSV infections (with 95% CI) detected by the quantitative PCR (RSV-A/B) will be tabulated by group. Descriptive analyses (mean,

median, min, max) of viral load assessed by the quantitative RT-PCR (RSV-A/B) of those asymptomatic RSV infections will also be done by group.

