**Table 5 Case definition of RSV- RTI/LRTI**

RSV infection	Symptomatic and/or asymptomatic RSV infection
RSV-RTI	Runny nose OR blocked nose OR cough AND Confirmed RSV infection 
RSV-LRTI	History of cough OR difficulty breathing  AND SpO 2 < 95%  , OR RR increase  AND Confirmed RSV infection 
RSV-severe LRTI	Meeting the case definition of RSV-LRTI AND SpO 2 < 93%  , OR lower chest wall in-drawing
RSV-very severe LRTI	Meeting the case definition of RSV-LRTI AND SpO 2 < 90%  , OR inability to feed, OR failure to respond / unconscious
RSV hospitalization	Confirmed RSV infection  AND Hospitalized for acute medical condition 
All-cause LRTI	History of cough OR difficulty breathing  AND SpO 2 < 95%  , OR RR increase 

Definition based on [Modjarrad, 2016]

LRTI = lower respiratory tract infections; RR = respiratory rate; RTI = respiratory tract infections;

SpO2 = blood oxygen saturatin

 Based on history reported by parents/LARs and includes difficulty breathing (e.g. showing signs of wheezing or stridor, tachypnoea, flaring [of nostrils], chest in-drawing, apnoea) associated with nasal obstruction

 For blood oxygen saturation (SpO2), the lowest value monitored will be used

 RR increase defined as ≥ 40/minute (12 months of age or above)

 RSV infection confirmed on nasal swab positive for RSV A or B by quantitative Reverse Transcription Polymerase Chain Reaction (qRT-PCR)

 RSV sampling and testing is based on medical judgment of medical practitioner or driven by algorithm

 Hospitalization is defined as a medical decision that the infant requires admission for observation or treatment

- For the analysis of RSV-RTI episode, the start date of an RTI episode will be defined as the first day of any occurrence of cough, runny nose, blocked nose, and a new case requires an interval of at least 7 symptom free days since the last episode of RTI that was diagnosed.
- For the analysis of RSV-LRTI or severe or very severe LRTI the start date of the LRTI episode is defined as the point at which the first symptoms of cough, or difficulty breathing were observed and a new case requires an interval of at least 7 symptom free days since the last episode of LRTI that was diagnosed.

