RSV-Ld = Low dose ChAd155-RSV vaccine ( $5 \times 10^9$  vp)  
 RSV-Md = Middle dose ChAd155-RSV vaccine ( $1.5 \times 10^{10}$  vp)  
 RSV-Hd = High dose ChAd155-RSV vaccine ( $5 \times 10^{10}$  vp)  
 Placebo-Ld = Non-active control (0.5 ml)  
 Placebo-Md = Non-active control (0.15 ml)  
 Placebo-Hd = Non-active control (0.5 ml)  
 PRE= Pre-vaccination at Day 1  
 PI(D31) = Post-vaccination dose 1 at Day 31  
 PII(D61) = Post-vaccination dose 2 at Day 61  
 PII(D366) = Post-vaccination dose 2 at Day 366

Note: This graph is provided as an example. Template will be adapted to display the 3 RSV or 3Control groups together and the 4 timepoints: PRE, PI(D31), PII(D61) and PII(D366).

Please note – To present the information on pooled RSV and pooled Placebo after looking at the data of Day 61 analysis.

**Figure 6 Co-expression profile of the RSV <F/N/M2-1> specific <CD4+> T-cells expressing at least two markers among CD40L, IL-2, TNF- $\alpha$ , and IFN- $\gamma$  in <RSV-Ld group> <PPS for analysis of immunogenicity at Day X>**

RSV-Ld = Low dose ChAd155-RSV vaccine ( $5 \times 10^9$  vp)  
 RSV-Md = Middle dose ChAd155-RSV vaccine ( $1.5 \times 10^{10}$  vp)  
 RSV-Hd = High dose ChAd155-RSV vaccine ( $5 \times 10^{10}$  vp)  
 Placebo-Ld = Non-active control (0.5 ml)  
 Placebo-Md = Non-active control (0.15 ml)  
 Placebo-Hd = Non-active control (0.5 ml)

Note: This graph is given as an example. Template will be adapted to display Q1-Median-Q3 for each combination of at least 2 markers out of (CD40L, IL-2, TNF- $\alpha$ , and IFN- $\gamma$   $\rightarrow$  11 combinations) for each timepoint: PRE, PI(D31), PII(D61) and PII(D366). It will be generated for each vaccine group and each RSV pool of peptides (RSV F/N/M2-1).

**Template 43 Number and percentage of subjects with at least one RSV infection, RSV-RTI, RSV-LRTI, RSV-severe LRTI, RSV-very severe LRTI, All-cause LRTI and RSV hospitalization from vaccination dose 1 up to D366/D731 visit <Exposed Set>**

	Group N =					Total N =				
	n**	n	%	95% CI		n**	n	%	95% CI	
Categories	n**	n	%	LL	UL	n**	n	%	LL	UL
No Infection										
RSV infection - symptomatic or asymptomatic*										
RSV-RTI										
RSV-LRTI										
RSV-severe LRTI										
RSV-very severe LRTI										
All-cause LRTI										
RSV hospitalization §										

RSV-Ld = Low dose ChAd155-RSV vaccine (5 x 10^9 vp)

RSV-Md = Middle dose ChAd155-RSV vaccine (1.5 x 10^10 vp)

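### The SAP omits two of the protocol's three all-cause respiratory analyses (all-cause RTI and all-cause severe LRTI) without declaring it, and the protocol no longer defines either term

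*SAP*

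**What the plan says.** Protocol 11.10, after the RSV-confirmed analyses, turns to illness irrespective of cause: "The incidence rate of all-cause RTI (with 95% CI) will be calculated by group". It continues: "The same descriptive analysis will be performed for all cause LRTI and all cause severe LRTI". Both are also to be presented by viral aetiology from the multiplex PCR.

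SAP 6.3 sets the scope of the corresponding analysis: "The analysis will be performed according to all case definitions presented in" SAP Table 5. That table holds seven definitions: RSV infection, RSV-RTI, RSV-LRTI, RSV-severe LRTI, RSV-very severe LRTI, RSV hospitalization and All-cause LRTI. Both severe classes begin with the condition "Meeting the case definition of RSV-LRTI", and RSV-LRTI in turn requires a nasal swab positive by qRT-PCR (footnote 4).

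The main summary table, Template 43, is titled "Number and percentage of subjects with at least one RSV infection, RSV-RTI, RSV-LRTI, RSV-severe LRTI, RSV-very severe LRTI, All-cause LRTI and RSV hospitalization". Template 44 repeats those categories by number of events. Neither has a row for all-cause RTI or all-cause severe LRTI, and Templates 45 to 54 add none. SAP Section 9, which records changes from the planned analyses, does not mention either.

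**The concern.** Protocol 1.2.4.4 explains the respiratory surveillance by the risk of enhanced RSV disease, and says it is meant to allow RSV-associated LRTI and severe LRTI to be described in the vaccine and placebo groups. All-cause severe LRTI supports that description. It is the planned case-definition severity comparison that does not require virological confirmation, so it guards against a group difference being hidden by missing, late or negative swabs. The protocol foresees some episodes without a swab: "In the event that it is not possible to schedule an assessment visit, which may arise if the family have travelled", the eCRF assessment page is completed from medical records (Section 9.2.1, and likewise 9.2.3).

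A planned safety comparison that disappears between protocol and SAP without an entry in the change section cannot be told apart, later on, from one dropped after the data were seen.

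**Working it through.** The documents give no sample size, power or event figure for this analysis, so there is no stated number to reproduce. The check is a reconciliation of texts, with simple arithmetic for scale.

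**Step 1. Planned against carried over.**

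| Protocol 11.10 analysis | Defined in current protocol Table 4 | In SAP Table 5 | Row in Templates 43 and 44 | Declared in SAP Section 9 |
|---|---|---|---|---|
| All-cause RTI | No | No | No | No |
| All-cause LRTI | Yes | Yes | Yes | Not needed |
| All-cause severe LRTI | No | No | No | No |

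One of three is kept and two are missing. None of the six changes in SAP Section 9 covers them. Those six concern cohort naming, day numbering, the design diagram, added Day 366 endpoints, immunogenicity on both sets, and the two-dose condition for the per-protocol set.

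**Step 2. Where the gap arose.** The Amendment 2 record in protocol Appendix D shows that Table 4 once carried all-cause RTI and all-cause severe LRTI definitions and was replaced by the present table, which has All-cause LRTI only. The same amendment edited other sentences of 11.10 and left the all-cause sentences in force. SAP Table 5 follows the current Table 4 and so inherits the gap.

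**Step 3. What happens to a severe LRTI without a qRT-PCR-positive swab.** It fails footnote 4, so it is not RSV-LRTI and therefore neither RSV-severe nor RSV-very severe LRTI. Other places where it could be seen:

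- Templates 43 and 44: counted as All-cause LRTI, with no severity.
- Template 50: counted by pathogen if the respiratory panel was run, with no severity.
- RSV hospitalization row: possible, because footnote 5 is looser ("RSV sampling and testing is based on medical judgment of medical practitioner or driven by algorithm"). This row is yes/no.
- SAE tables to Day 731 and the RSV-LRTI AESI table (SAP 6.4.1.1): by preferred term.
- Grade 3 unsolicited AE tables: investigator intensity, for 30 days after each of two doses. That is 2 × 30 = 60 of 730 days, or 60/730 = 8%.
- Templates 33 and 34: listings showing intensity, SpO2, respiratory rate and local test results.

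None of these assigns a severity class by the SpO2 and chest in-drawing definition.

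**Step 4. Scale.** Protocol 1.3 gives 32 to 48 vaccinees, with about as many on placebo. One infant is 1/32 = 3.1% or 1/48 = 2.1% of a pooled arm. With the SAP's Clopper-Pearson method, a restored row would show the following for assumed counts:

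| Infants with the event | n = 32 | n = 48 |
|---|---|---|
| 0 | 0 to 10.9% | 0 to 7.4% |
| 1 | 0.1 to 16.2% | 0.1 to 11.1% |

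The row would be imprecise, as are the RSV-confirmed rows beside it.

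**The case against.** The strongest reply is that the SAP did what the protocol's definitions allow. Current Table 4 defines All-cause LRTI only, the two 11.10 phrases look like leftovers from Amendment 2, and the secondary endpoints (RSV-RTI, RSV-LRTI, severe RSV-LRTI) are all kept in SAP 4.2. Protocol 11.12 also allows deviations to be explained in the final report. This stands as an account of the cause, and it means the repair must write definitions as well as restore rows. It does not settle the matter: 11.10 is current text, and SAP Section 9 exists to declare such changes beforehand.

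A reader might infer that a severe case without a positive central swab would be invisible. The documents do not support that. Hospitalized LRTIs are SAEs, the RSV-LRTI AESI rests on investigator judgment and local testing (Protocol 9.1.5.2), the RSV hospitalization row does not use footnote 4, and listings cover a trial of at most 96 infants. What is missing is severity by case definition, not the case itself. The IDMC also receives AESIs within 48 hours and cumulative RSV reports about monthly, so real-time monitoring does not depend on these tables.

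A reader might also infer that unswabbed cases are mainly the urgent ones. A note to Protocol Figure 3 does mention urgent care as an example. However, 9.2.4 allows the assessment visit to take place at the emergency location, and 9.2.5 calls for a swab in every child hospitalized with RTI. The number of ungraded cases, and how severe they would be, cannot be estimated from the documents. Some children without a positive swab will simply have non-RSV illness and are rightly outside the RSV severity counts.

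Counting locally confirmed RSV in an extra sensitivity row is likewise tempting, but neither document plans it.

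**Conclusion.** The discrepancy is real. Two of the three all-cause analyses in current protocol 11.10 are absent from the SAP and undeclared, and the protocol itself is inconsistent because 11.10 asks for terms that Table 4 no longer defines. The consequence is limited: an LRTI with severity signs but no qRT-PCR-positive swab is ungraded in the case-definition tables, though it may be seen elsewhere. Each such infant would be 2.1 to 3.1 percentage points of a pooled arm. How many there would be is unknown.

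The analysis is descriptive, so no endpoint, sample size or error rate changes. The conclusion rests on reading 11.10 as still intended. If it is not, the fault is an unreconciled protocol sentence and an undeclared omission. Either way it should be corrected before the Day 366 analysis, which is the first to include the RSV and RTI tables (SAP Table 3).

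**What to change.** Add two analysis definitions to SAP Table 5:

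- All-cause RTI: the RSV-RTI symptoms without the RSV confirmation.
- All-cause severe LRTI: All-cause LRTI plus the current Table 4 severe signs, without the RSV confirmation. State whether a child meeting only the very severe signs is included, since Table 4 does not nest that class within the severe one.

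Add both rows to Templates 43 and 44, by group and pooled, and read them beside the RSV-confirmed rows because they include non-RSV illness. Note that aetiology for all-cause RTI will be incomplete: under protocol Table 13 the panel is run only on RSV-positive swabs and confirmed LRTI.

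If the sponsor does not intend these analyses, reconcile protocol 11.10 with Table 4, and declare and justify the removal in SAP Section 9.

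The cost is two definitions and a few table rows from signs already collected in the eCRF. The rows will not recover every case: where an episode was recorded from medical records alone, SpO2 or chest in-drawing may also be missing.
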